#### 9.5. Combination of tDCS and GT (Experiment 3)

Experiment 3 will include the tDCS and GT approaches described above in a 2 by 2 crossed design with four cohorts: active tDCS and gaze training, active tDCS without gaze training, gaze training with sham tDCS or just sham tDCS. For each of the interventions, the most effective parameter will be chosen (implicit or explicit for gaze training, and bilateral or vertex tDCS), based on the results from the two previous experiments.

This protocol will unfold in the same manner, and under the same schedule as described for Experiments 1 and 2, except that participants will be exposed to different combinations of interventions and will be asked to return for a 4-6 week follow up visit in which they only perform the FLS modules without intervention (no tDCS or GT).

In regard to the interventions outlined here, [name], the General Surgery Research Fellow in charge of all enrollment and participation, has all necessary training for tDCS and eye tracker technology to ensure these are used safely and administered according to proper procedures.

## **10. Risk/Benefit Assessment**

There are no more than minimal medical or psychological risks associated with this research.

### 10.1. Gaze Training

There are no known significant adverse effects of gaze training. The only anticipated adverse event is the potential for discomfort from the wearable gaze tracking equipment. Participants will be asked to report any discomfort immediately to the study staff and proper steps will be taken to adjust or pad the headset with gauze to relieve discomfort.

### 10.2. tDCS

Since the development of tDCS in the 1960's, thousands of subjects have participated in studies and received tDCS without any substantial adverse effects. There has been no evidence of neuronal damage induced by tDCS: Nitsche and Paulus (2001) and Nitsche et al. (2003) found no elevation of neurone-specific enolase (sensitive marker of neuronal damage). McCreery et al. (1990) demonstrated that current densities below  $25\text{mA/cm}^2$  do not induce brain tissue damage even by applying high-frequency stimulation over several hours. In our protocol, we stimulate with a maximum current density of approximately  $0.03\text{ mA/cm}^2$ , a thousand fold below this limit. Duration of stimulation is an additional factor contributing to potential tissue damage, which has been detected at a minimum total charge of  $216\text{ C/cm}^2$  (Yuen et al., 1981). This protocol exposes subjects to maximum total charges of  $0.02\text{ C/cm}^2$ , which is far below the established safety threshold.

Within these parameter ranges tDCS has been shown to be a safe and tolerable minimally invasive technique. Nonetheless, commonly observed adverse effects of tDCS are skin irritation that may occur at the site of the tDCS electrodes, including reddening of the skin and itching under the electrode sites while the current is on. To minimize chemical reactions at

the electrode-skin interface, non-metallic, conductive rubber electrodes, covered completely with saline-soaked sponges will be used, as recommended by Nitsche and Paulus, 2000.

In order to reduce these minimal risks, the impedance of the tDCS system will be continuously monitored on a visible LED display throughout all training sessions. In addition, the stimulator device has an automatic shut-off switch that shuts off current when impedances exceed the safety guidelines.

Electrode positioning with good skin contact will be ensured by the experimenter and the sponges will be re-wetted during breaks and as needed.

Our group has extensive experience administering tDCS, as well as other more invasive forms of neuromodulation. These activities are described in Duke SOM IRB protocols; Pro00065334 “Using TMS to increase executive function in older adults”, Pro00064107 “PAS in Healthy Subjects”, and Pro00069059 “TMS\_INS”.

A member of the research team will be present at all times to monitor patient safety, and standard procedure will be followed whenever an adverse event is recorded. [name], General Surgery Vice-chair of Research and Director of SEAL, will be available as study doctor for the duration of this protocol.

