## 9.2. Transcranial Direct Current Stimulation (tDCS) Procedure (Experiment 1)

Transcranial direct current stimulation is a noninvasive neuromodulatory technique that delivers constant, low-intensity, direct current to cortical areas via electrodes placed on the scalp. Over the past 10 years, numerous studies have shown that this approach can be used

to facilitate or inhibit spontaneous neuronal activity and there are a growing number of studies that have demonstrated tDCS can enhance motor learning in healthy individuals as well as speed recovery in clinical populations. Further, the ease with which tDCS can be implemented and tolerated, paired with the lasting changes in cortical excitability it induces, gives this approach powerful potential to facilitate surgical skill learning.

Participants in this study will be randomly assigned to receive one of four tDCS conditions (2 electrode configurations, each with active or sham) administered using the Soterix 1x1 clinical trial device. All individual tDCS stimulations will take place in 20-minute blocks, with a 5-minute break between each block. Current will be delivered through saline-soaked sponges (3 cm x 5 cm) that will be re-wetted with saline when needed during the experiment and in the breaks between blocks to prevent skin irritation and increase impedance.

There will be two active tDCS conditions:

1. Bilateral configuration tDCS, with anode over the left motor cortex, and cathode over the right motor cortex, corresponding to C3 and C4 10-20 EEG sites, respectively;
2. Supplemental motor area (SMA) configuration tDCS, with anode over the SMA (3 cm anterior to the vertex), and cathode over midline prefrontal cortex (Fpz).

The two sham tDCS conditions will utilize the same two electrode configurations (50% of each across participants). In both active and sham conditions, the current will be initially increased in a ramp-like fashion over 30 seconds until reaching 2 mA. During the active conditions, the current will be maintained for 20 minutes, while in the sham condition it will be turned off after 30 s. This initial current ramp-up allows us to reproduce the perceived sensations on the skin (tingling, fade) induced by the active tDCS and thus, create an effective placebo condition.

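### Sections 9.2 and 10.2 disagree on tDCS exposure: the settings in 9.2 give 4.4 times the current density and 8 times the charge per block stated in the risk section

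*Combined protocol and SAP*

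**What the plan says.** Section 9.2 gives the only stimulation settings in the document. On electrodes: "Current will be delivered through saline-soaked sponges (3 cm x 5 cm", an area of 15 cm². On current: "the current will be initially increased in a ramp-like fashion over 30 seconds until reaching 2 mA". On duration: "During the active conditions, the current will be maintained for 20 minutes". On scheduling: "All individual tDCS stimulations will take place in 20-minute blocks, with a 5-minute break between each block". Section 4 describes 40-minute training sessions in Experiment 1, three per participant, so a session holds two blocks.

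Section 10.2 then quantifies the exposure for the risk assessment. It states "In our protocol, we stimulate with a maximum current density of approximately" 0.03 mA/cm², described as "a thousand fold below this limit", where the limit is 25 mA/cm². It continues: "This protocol exposes subjects to maximum total charges of" 0.02 C/cm², set against a cited damage threshold of 216 C/cm². The next paragraph opens: "Within these parameter ranges tDCS has been shown to be a safe and tolerable minimally invasive technique".

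**The concern.** Current density is current divided by electrode area, and charge density is current density multiplied by time. Section 9.2 supplies all three inputs, so both figures in 10.2 should follow from it directly. Neither does, and both fall on the reassuring side of what 9.2 implies.

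These are the only computed exposure figures in the risk section of an IRB summary, and the tolerability statement that follows appears to lean on them. If 9.2 is right, participants receive more than the stated maxima and the stated safety margin is too large. As the document stands, an IRB reader cannot tell which exposure was approved. Section 9.5 carries the same tDCS procedure into Experiment 3, so the discrepancy carries over too.

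**Working it through.** **Inputs.** From section 9.2: current 2 mA; area 3 × 5 = 15 cm²; duration 20 min = 1200 s per block. From section 10.2: stated density 0.03 mA/cm²; stated charge 0.02 C/cm²; cited limits 25 mA/cm² and 216 C/cm².

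**The plan's own margins.** 25 / 0.03 = 833, which is loosely the thousand-fold margin claimed. 216 / 0.02 = 10,800. The wording in 10.2 was therefore written around 0.03, and a misread digit is an unlikely explanation for the density.

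**Recomputed from section 9.2.**

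| Quantity | Calculation | Result | Ratio to stated value | Margin to cited limit |
|---|---|---|---|---|
| Density | 2 mA / 15 cm² | 0.133 mA/cm² | 0.133 / 0.03 = 4.4 | 25 / 0.133 = about 188-fold |
| Charge, one block | 0.002 A × 1200 s / 15 cm² | 0.16 C/cm² | 0.16 / 0.02 = 8 | 216 / 0.16 = 1350-fold |
| Charge, two-block session | 2 × 0.16 | 0.32 C/cm² | 0.32 / 0.02 = 16 | 216 / 0.32 = 675-fold |

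The last row sums charge across the 5-minute break. Section 10.2 does not say whether its total is per block, per session or per course. One block is the reading most favourable to the plan.

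**Ramp.** A linear 30 s ramp delivers the equivalent of 15 s at full current, or 0.133 mA/cm² × 15 s = 0.002 C/cm². The block total is 0.158 C/cm² if the ramp falls inside the 20 minutes and 0.162 if it is added, so the ratio is 7.9 to 8.1.

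**Rounding.** If 0.03 stands for anything from 0.025 to 0.035, the density ratio is 5.3 to 3.8. If 0.02 stands for 0.015 to 0.025, the per-block charge ratio is 10.7 to 6.4. Neither gap closes.

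**Consistency within section 10.2.** 0.03 mA/cm² × 1200 s = 0.036 C/cm², which is 1.8 times the stated 0.02. At the rounding limits, 0.025 mA/cm² × 1200 s = 0.030 C/cm² against at most 0.025, still a factor of 1.2.

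**Could one correction to section 9.2 rescue both figures?**

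- Keeping 2 mA and 20 minutes, the density needs an area of 2 / 0.03 = 66.7 cm². The charge needs 2.4 C / 0.02 = 120 cm². With rounding these become 57 to 80 cm² and 96 to 160 cm², which do not overlap.
- Keeping 15 cm² and 20 minutes, the density needs 0.03 × 15 = 0.45 mA. The charge needs 0.02 × 15 / 1200 s = 0.25 mA.

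No single electrode size or current gives both figures for a 20-minute block.

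**The case against.** The strongest reply concerns consequence, since the arithmetic is not in dispute.

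- **The operative conclusion survives.** Section 10.2 argues that exposure is far below the cited thresholds, and at about 188-fold for density and 1350-fold per block for charge it still is. The risk assessment also rests on experience with tDCS, continuous impedance monitoring, automatic shut-off and a staff member being present, none of which depends on 0.03 or 0.02. All of this stands.
- **The direction of error is unknown.** The documents do not show which section is wrong. If 9.2 misdescribes the electrode or current, the 4.4 and 8 could disappear. This also stands, and the multiples are conditional on 9.2. What would remain is the conflict inside 10.2, which is smaller and sensitive to rounding but does not vanish.
- **The stated figures are approximate.** Both have one significant digit, so the multiples should be read with the rounding ranges above. That is fair, but no rounding removes either gap.
- **The parameter ranges may mean the cited limits.** The sentence "Within these parameter ranges tDCS has been shown to be a safe and tolerable minimally invasive technique" could refer to anything below 25 mA/cm² and 216 C/cm², in which case it is not undermined. The wording allows this, though the more natural reference is to the protocol's own parameters, stated immediately before.

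It could be argued that this is only a wording correction. Against that, it concerns the only quantitative exposure figures put to the IRB, and both look lower than the protocol's own settings imply.

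**Conclusion.** The concern holds: the exposure figures in section 10.2 cannot be obtained from the settings in section 9.2. If 9.2 is right, density is understated 4.4-fold (3.8 to 5.3 allowing for rounding) and charge per block 8-fold (6.4 to 10.7), and the claimed thousand-fold margin is about 188-fold. Whichever section is in error, at least one figure in 10.2 is wrong for a 20-minute block. The result assumes that the sponge dimensions give the contact area and that current is held at 2 mA for the full block.

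This is a misstated risk section. It is not evidence of unsafe stimulation by the thresholds the protocol cites, and sample size and efficacy analyses are untouched. It should be fixed.

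**What to change.** 1. Confirm the electrode size and current actually used, and correct section 9.2 if it misdescribes them.
2. Recompute density and charge from the confirmed settings and replace both exposure figures and the thousand-fold claim in section 10.2, stating the basis as per block and per session.
3. If 9.2 stands, the text should read 0.133 mA/cm² (about 188-fold below 25), 0.16 C/cm² per block (1350-fold below 216) and 0.32 C/cm² per two-block session (675-fold below).
4. Notify the IRB, and change the consent text only if it uses these figures.

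The cost is a wording change and an IRB amendment. If 9.2 is right, the stated safety margin also becomes less favourable. No change to dose, procedures or analysis is needed.

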### 10.3 Reproductive Risks

All female subjects of child-bearing age will undergo a urine pregnancy test. If positive, that individual will be excluded from the study.

### 10.4 Benefits

Subjects have the ability to benefit from participating in this study due the exposure to laparoscopic surgical skills and the FLS curriculum. They will gain repetitions on FLS tasks that are required to be board certified in surgery. Pending the subjects' career goals, this could have a positive impact on their future.

## **11. Costs to the Subject**

There will be no charge to subjects for any of the tests, procedures, or professional services related to this study.

### **13. Data & Safety Monitoring**

The subjects will be fully informed of the nature of the study requirements prior to enrollment and periodically throughout the study. The subject's wellbeing will be continuously monitored by the experimenter, and the Principal Investigator will report all serious adverse events in an expedited manner to the Duke University Health System (DUHS) Institutional Review Board (IRB) office and all applicable regulatory authorities in accordance with the Center's standard operating procedures.

The study monitor will be the PI, [name]. [name] will ensure the quality of the study and establish that all operations are complying with the investigational plan and IRB regulations. In accordance with federal regulations the PI will monitor for, review, and promptly report to the IRB, appropriate institutional officials, sponsor, coordinating center and the appropriate regulatory agency head all unanticipated problems involving risks to subjects or others that occur in the course of a subject's participation in a research study (45 CFR 46.103(b)(5)(i) and 21 CFR 56.108(b)(1)), and all reportable AEs will be submitted per the DUHS IRB policies. Monitoring of this protocol is simplified by the fact that this study involves a small number of investigators and a single facility in which the study is being conducted.

Throughout the investigation, the monitor will ensure that the facilities being used continue to be acceptable for the purposes of the study, that the investigational plan is being followed, that any changes to the protocol have received IRB approval and have been reported to the sponsor, that accurate, complete, and current records are maintained, that accurate, complete, and timely reports are made to the IRB. This will be accomplished through quarterly meetings during which the status of the protocol, investigators, and IRB compliance are reviewed. The monitor will review each research chart for completeness and accuracy. He will confirm that inclusion and exclusion criteria have been met for each subject enrolled, and compliance with all other aspects of the investigational plan are met.

### **14. Privacy, Data Storage & Confidentiality**

Section 12 of the e-IRB submission form has been completed.
